7.4. Potential Risks of Human Use

Increases in hematologic parameters (RBC, hemoglobin, hematocrit, reticulocytes) are expected pharmacologic effects of ACE-536 treatment. Increases in systolic and diastolic blood pressures may occur in concert with increases in hemoglobin values. Excessive or rapid increases in hemoglobin or blood pressure may occur and will be monitored. Dose modifications rules for individual subjects and dose escalation/reduction rules will be utilized to minimize risks associated with increased RBC parameters.

Adverse events observed in the Phase 1 study in healthy volunteers that were considered probably or possibly related to study drug included injection site hemorrhage, injection site macule, dry skin, hyperesthesia, muscle spasms, myalgia, generalized pruritis, and papular rash.

Membranoproliferative glomerulonephritis was observed in both rats and monkeys, likely secondary to immune complex deposition. These findings were associated with increases in serum BUN and creatinine. The presence of immune complexes in renal tissue from monkeys treated with ACE-536 was demonstrated by immunohistochemistry.

The growth of heart and lungs was slightly reduced in rats exposed to ACE-536 as compared with control animals; these decreased heart and lung weights were reversible and there was no

corresponding histology finding. These findings were not replicated in the monkey toxicology studies; the potential for these adverse effects in humans is unknown.

Based on rat toxicology studies, treatment with ACE-536 may affect the adrenal gland. These findings were specific to the rat as they were not replicated in the monkey toxicology studies.

As with all biologics, there is the potential for anti-drug antibodies that can be associated with increased drug clearance and hypersensitivity reactions. Anti-drug antibody formation against ACE-536 as well as human ActRIIB protein will be monitored in the initial clinical studies.

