14. ASSESSMENT OF SAFETY

14.1. Adverse Event Definitions

Adverse Event

An adverse event (AE) is any untoward medical occurrence in a patient or clinical investigation patient administered a study drug, which does not necessarily have a causal relationship with this treatment. An AE can therefore be any unfavorable and unintended sign (including an abnormal laboratory finding), symptom, or disease temporally associated with the use of the study drug whether or not it is considered related to the study drug.

Abnormal laboratory and other abnormal investigational findings (e.g., physical exam, ECG) should not be reported as AEs unless they are associated with clinical signs and symptoms, lead to treatment discontinuation, or are otherwise considered clinically relevant by the investigator. In cases of surgical or diagnostic procedures, the condition/illness leading to such a procedure is considered as the AE rather than the procedure itself. In case of a fatality, the cause of death is considered as the AE, and the death is considered as its outcome.

Unexpected Adverse Events

An unexpected AE is an AE that is not described in nature or severity in the Investigator's Brochure.

Events Not to Be Considered as Adverse Events

Pre-existing medical conditions/signs/symptoms present before the Screening period that do not worsen in severity or frequency during the study are defined as Baseline Medical Conditions, and are not to be considered AEs. Anticipated day-to-day fluctuations of pre-existing conditions, including the disease under study, that do not represent a clinically significant exacerbation or worsening need not be considered adverse events.

Serious Adverse Event

A serious adverse event (SAE) is any AE, occurring at any dose level/regimen and regardless of causality that:

- Results in death.
- Is life-threatening: Life-threatening means that the patient was at immediate risk of death from the reaction as it occurred (i.e., it does not include a reaction which hypothetically might have caused death had it occurred in a more severe form).
- Requires inpatient hospitalization or prolongation of existing hospitalization; however, a hospitalization for an elective procedure will not be considered an SAE.
- Results in persistent or significant disability/incapacity.

- Is a congenital anomaly/birth defect.

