3.2. Treatment Discontinuation

Patients were informed that they have the right to withdraw from the study at any time for any reason without prejudice to their medical care.

A patient may be discontinued from treatment for any of the following reasons:

- Patient's request
- Patient's unwillingness or inability to comply with the protocol
- Pregnancy
- Use of prohibited medication (e.g., hydroxyurea)
- Medical reason or adverse event, at the discretion of the investigator and/or the medical monitor
- Hypersensitivity reaction to study drug
- At the discretion of the sponsor (e.g., termination of the study or a dose level)

A patient may be withdrawn from the study for any of the following reasons:

- Patient's request
- Patient's unwillingness or inability to comply with the protocol
- Death
- Loss to follow-up
- At the discretion of the sponsor (e.g., termination of the study)

Patients who discontinued treatment early completed the end of treatment (EOT) follow-up visit at the time of discontinuation and then completed the end of study (EOS) follow-up visit approximately 28 days later.

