5. STATISTICAL METHODOLOGY

5.1. Definitions

Transfusion Dependent (TD)

Based on protocol, TD patients are defined as those who required ≥ 4 units of RBCs every 8 weeks (confirmed over 6 months prior to Cycle 1 Day 1).

For programming implementation, a patient is defined as TD if the total RBCs is ≥ 11 units during 26 weeks on or prior to Cycle 1 Day 1.

Non-Transfusion dependent (NTD)

NTD patients are those who do not meet the above definition for TD. For programming implementation, NTD patients are defined as those who received < 11 units of RBCs during 26 weeks on or prior to Cycle 1 Day 1.

Baseline Hemoglobin

Baseline hemoglobin will be an average of hemoglobin measurements within 28 days of Cycle 1 Day 1, excluding measurements within 14 days following RBC transfusion.

Baseline Transfusion Burden

Baseline transfusion burden will be calculated as the total amount of RBC transfusions during the 12 weeks on or prior to Cycle 1 day 1.

Baseline for Other Parameters

Baseline erythropoietin (EPO) is defined as the maximum test value within 28 days of Cycle 1 Day 1. For all other parameters, baseline is defined as the last observation on or prior to Cycle 1 Day 1.

Transfusion Unit Conversion

The transfusion amount measured in unit “mL” will be converted to “units” according to medical review.

End of Treatment (EOT)

Procedures and evaluations for the end of treatment visit should be performed 28 days (± 7 days) after the last dose of ACE-536.

End of Study (EOS)

Procedures and evaluations for the end of study visit should be performed 28 days (± 7 days) after the Day 113/EOT visit (56 days after the last dose of ACE-536).

Combined Dose Groups

Low dose group includes patients on 0.2mg/kg and 0.4 mg/kg dose cohorts. High dose group include patients with dose level 0.6 mg/kg and above. Suitable summaries may be presented by low/high dose as specified.

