5.8.3. Laboratory Evaluations

Results from the following laboratory parameters, recorded at their respective time points will be summarised by dose cohort and time point:

Haematology: (Screening, Days 1, 8 and 15 of each cycle, End of Treatment, Post Treatment Follow Up and End of Study).

RBC, WBC with differential, hemoglobin, hematocrit, haptoglobin (optional), reticulocyte count, platelet count, MCV, MCH, MCHC, RDW, and nRBCs

Chemistry: (Screening, Days 1 and 15 of Cycle 1, and Days 1 of each subsequent cycle, End of Treatment and End of Study).

Sodium, potassium, chloride, carbon dioxide/bicarbonate (optional), AST, ALT, lactate dehydrogenase (LDH), total bilirubin, indirect bilirubin, alkaline phosphatase, blood urea nitrogen (BUN)/urea, creatinine, GGT, calcium, phosphorus, glucose, amylase, lipase, total protein, albumin, and uric acid

Urine: (Day 1 of Cycles 1, 2 and 4, End of Treatment and End of Study).

PH, specific gravity, protein, glucose, ketones, blood, leukocyte esterase, and nitrite, with microscopic examination if indicated; Microalbumin and creatinine

Urine Chemistry: (Day 1 of Cycles 1, 2 and 4, End of Treatment and End of Study).

Microalbumin and creatinine will be performed by the central lab.

Categorical and numeric variables will be presented separately.

Actual values and changes in haematology and biochemistry laboratory values from baseline will be summarised by dose cohort and by time point.

Shift tables for the haematology and biochemistry laboratory parameters comparing values above, within and below the normal reference range at baseline to the end of treatment visit will be presented using standard reference ranges.

Actual urine laboratory values will be summarised by dose cohort.

Peripheral blood smears are taken at Screening, Day 1 of Cycles 1, 2, and 5 and at the end of treatment visit. These data will be listed only.

All laboratory values will be listed for all patients.

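### The laboratory shift tables compare baseline with the End of Treatment visit only, so patients who left the normal range during treatment and recovered are not counted at any dose

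*SAP*

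**What the plan says.** SAP 5.8.3 plans one kind of laboratory shift table, for haematology and biochemistry. Its defining sentence ends "below the normal reference range at baseline to the end of treatment visit will be presented using standard reference ranges". Baseline for these parameters comes from SAP 5.1: "For all other parameters, baseline is defined as the last observation on or prior to Cycle 1 Day 1" (haemoglobin and erythropoietin have their own rules).

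EOT timing depends on how the patient left treatment. For completers, SAP 5.1 states: "Procedures and evaluations for the end of treatment visit should be performed 28 days (± 7 days) after the last dose of ACE-536". For the rest, SAP 3.2 states: "Patients who discontinued treatment early completed the end of treatment (EOT) follow-up visit at the time of discontinuation".

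Three other outputs carry laboratory data:

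- Actual values and changes for haematology and biochemistry are summarised by cohort and time point. Under SAP 5.2 these summaries include the minimum and maximum.
- All laboratory values are listed for every patient.
- AE tables take in a laboratory finding only under the rule in Protocol 14.1, which begins "Abnormal laboratory and other abnormal investigational findings (e.g., physical exam, ECG) should not be reported as AEs unless". The exceptions that follow are findings with clinical signs and symptoms, findings that lead to treatment discontinuation, and findings the investigator considers clinically relevant.

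For urine, SAP 5.8.3 says "Actual urine laboratory values will be summarised by dose cohort" and plans neither change nor shift. Protocol 15.2.3 says that changes from baseline in clinical laboratory values will be summarised over time. Protocol 7.4 lists membranoproliferative glomerulonephritis in rats and monkeys among the potential risks and adds: "These findings were associated with increases in serum BUN and creatinine".

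**The concern.** A shift table exists to show how many patients at each dose moved from inside the normal range to outside it. Tying it to one visit after dosing has stopped means that a completer's excursion during Cycles 1 to 5 counts only if it is still present at EOT. If it has resolved, the table reports no shift.

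The error can go only one way. Leaving visits out can lower the number of patients shown as having moved out of range, but cannot raise it. Safety and tolerability is a secondary objective of an ascending-dose study, and the laboratory profile by dose is one of the things a reader will want from the report. The EOT column also mixes two kinds of visit: about four weeks off dosing for completers, and the day of stopping for everyone else.

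The urine gap is separate. Kidney findings are the toxicology signal for which urine protein and microalbumin/creatinine are most relevant, yet these are the parameters with no within-patient comparison at all.

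**Working it through.** There is no stated figure to reproduce, so the check is a count of visits and a comparison of outputs.

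**EOT day for a patient on schedule.** Last dose on Day 85, plus 28 days, gives Day 113, which matches the schedule of events.

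**Haematology visits after baseline** (SAP 5.8.3 and the schedule):

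- On treatment: Days 8 and 15 of Cycle 1 (2), plus Days 1, 8 and 15 of Cycles 2 to 5 (3 × 4 = 12), giving 14.
- After treatment: EOT and EOS, giving 2.
- Total 14 + 2 = 16. The shift table uses 1 of 16 (6%), and for completers 0 of 14 on treatment.

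SAP 5.8.3 also names a post-treatment follow-up visit for haematology. The schedule has no such column apart from EOT and EOS, so it is not counted.

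**Chemistry visits after baseline:**

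- On treatment: Days 15, 22, 43, 64 and 85, giving 5.
- After treatment: Days 113 and 141, giving 2.
- Total 5 + 2 = 7. The shift table uses 1 of 7 (14%), and for completers 0 of 5 on treatment.

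A patient who goes straight into the extension study may skip EOS (SAP 3.3). The totals are then 16 − 1 = 15 and 7 − 1 = 6; the on-treatment counts do not change.

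**Urine visits after baseline:** Day 1 of Cycles 2 and 4, EOT and EOS, giving 4. None enters a change or shift table.

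**Does another output supply the missing count?**

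| Output | What it shows on treatment | What it does not show |
|---|---|---|
| By-visit summaries | Extreme value and extreme change at each visit | Whether that patient was in range at baseline; how many patients left the range |
| Listings | Every value | Any count by dose |
| AE tables | Changes that are symptomatic, lead to stopping, or are judged clinically relevant | Other excursions |
| Urine summaries | Actual values by cohort and time point | Any within-patient change |

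The first row matters because eligibility allows abnormal starting values: AST or ALT below 3 × ULN and creatinine up to 1.5 × ULN (Protocol 9.3.1). A by-visit maximum above the range may therefore have been present at baseline.

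**Comparison within the SAP.** ECG interpretation is tabulated as a change from baseline to each post-baseline visit (SAP 5.8.5), and AEs by maximum severity grade (SAP 5.8.2). The laboratory shift is the only one of the three limited to a single visit.

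**The case against.** The case against is substantial. In a cohort of 6, the by-visit minimum and maximum print the most extreme patient at each visit. Every value is listed. Clinically relevant laboratory changes must be recorded as AEs (Protocol 14.5) and then enter the tables by severity. Dipstick protein, if treated as categorical, is counted by category at each visit. The protocol promises shift tables only as appropriate, so the EOT choice for haematology and chemistry contradicts nothing. Escalation decisions rested on the Safety Review Team's review of laboratory results, not on these tables. For a patient who stops because of a laboratory problem, EOT at discontinuation may catch the value near the event.

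All of that stands, and it limits the point. It does not supply a count of patients per dose who moved out of range.

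A reader might also infer three stronger things that the documents do not support:

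- **That on-treatment excursions cannot be seen anywhere.** This is true of the shift tables only. Extremes and listings show them.
- **That EOT is close to washout.** With the Phase 1 half-life of 15.5 to 18.5 days (Protocol 7.3), elimination alone over 28 days leaves 0.5^(28/15.5) = 29% to 0.5^(28/18.5) = 35%. That ignores slow absorption and accumulation. A one-compartment model of the form in SAP 5.9.4, with the Phase 1 half-life, the Phase 1 Tmax of 7.7 to 11.7 days and five equal 3-weekly doses, puts Day 113 at about 44% to 59% of the overall peak. EOT is off dosing but not free of drug.
- **That a known share of excursions is missed.** If onset is uniform over the 112 days from Day 1 to Day 113, the share still present at Day 113 is duration/112. That is 7/112 = 6%, 21/112 = 19%, 56/112 = 50% and 84/112 = 75%. The documents give no duration, so no single figure can be defended.

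**Conclusion.** The point holds as a gap in tabulation. The haematology and biochemistry shift tables use 1 of 16 and 1 of 7 scheduled post-baseline visits. For completers they use none of the 14 and 5 on-treatment visits, and no other planned laboratory table counts patients who left the normal range and came back. For urine there is also a departure from Protocol 15.2.3, and the list of major changes in SAP 5.13 does not mention it.

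The visit counts assume a patient who follows the schedule through five cycles. How many patients would be reclassified cannot be estimated from the documents, because it depends on how long excursions last. Nor do the documents show that abnormal values are hidden from the report, or that AE recording leaves most of them out. This is a cheap improvement to a descriptive safety analysis, not a flaw that invalidates it.

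**What to change.** In SAP 5.8.3:

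1. Add a shift from baseline to the worst post-baseline value for haematology and chemistry, with separate tables for high and low, over all scheduled and unscheduled visits up to last dose + 56 days. State that the window closes earlier if the patient starts dosing in the extension study.
2. Add the same worst-value shift for dipstick protein category.
3. Add change from baseline by visit, and the worst post-baseline value, for urine microalbumin/creatinine.
4. Keep the baseline-to-EOT shift, labelled as showing recovery, and footnote that EOT is at discontinuation for early stoppers.
5. State which baseline haemoglobin uses in these tables, since SAP 5.1 gives it a separate definition.

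The cost is SAP wording, programming and a few more tables from data already collected. The drawback is that taking the worst of up to 16 values will produce more chance out-of-range results than a single visit. The report should say so and read the worst-value table alongside the EOT table and the listings.

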5.8.4. Vital Signs

Vital signs parameters include weight (kg), heart rate, systolic and diastolic blood pressure, respiratory rate, and temperature (°C). Vital signs are recorded at Screening and on Days 1, 8 and 15 of each cycle and EOT. For each parameter at each time point, the change from baseline to post baseline will be summarised by dose cohort. The baseline assessment is defined as the last measurement on or before Cycle 1 Day 1.

Plots of vital sign parameters for both mean observed and mean change from baseline will be presented by dose cohort for each parameter.

Vital signs will also be listed for all patients.

5.8.5. ECG Results

12 lead ECG results are recorded at Screening, Cycle 2 Day 1, and at the end of treatment visit. The quantitative ECG assessments (Ventricular rate, QRS width, PR interval, and QTc interval) will be summarised at each time point by dose cohort.

ECG overall interpretation (normal, abnormal not clinically significant and abnormal clinically significant) will be presented for actual values and changes from baseline (Screening observation) to each post baseline visit [expressed as Improvement, No Change, and Deterioration] by dose cohort.

Note:

- Improvement = Abnormal Clinically Significant (CS) to Abnormal Not Clinically Significant (NCS)/Normal, Abnormal NCS to Normal
- Deterioration = Normal to Abnormal NCS/CS, Abnormal NCS to Abnormal CS
- No change = Normal to Normal, Abnormal NCS to Abnormal NCS, Abnormal CS to Abnormal CS

If either result is missing for any subject, then an 'Unknown' category will be presented.

ECG results will be listed for all patients.

5.8.6. Physical Examination

A physical examination is conducted at Screening and on Day 1 of each cycle and at the end of treatment and end of study visits. Physical exam details will be listed only.

5.9. Pharmacokinetics Analysis

5.9.1. Pharmacokinetic Sampling Schedule

Blood samples for determination of ACE-536 serum concentrations are collected from all subjects at the following schedule:

Treatment/Follow Up	Visit	Study Day	PK Sample
Dose 1	Cycle 1 Day 1	1	X
	Cycle 1 Day 8	8	X
	Cycle 1 Day 11	11	X
	Cycle 1 Day 15	15	X
Dose 2	Cycle 2 Day 1	22	X
	Cycle 2 Day 8	29	X
Dose 4	Cycle 4 Day 1	64	X
	Cycle 4 Day 8	71	X
	Cycle 4 Day 15	78	X
Dose 5 (Final Dose)	Cycle 5 Day 1	85	X
	Cycle 5 Day 8	92	X
	Cycle 5 Day 15	99	X
Follow up Period	End of Treatment	113	X
	Post-Treatment Follow Up	141	X
	End of Study	169	X

Acceptable time windows for pharmacokinetic blood draws are \pm 1 day in Cycle 1, \pm 2 days in Cycles 2 to 5, and \pm 7 days in the follow-up period.

5.9.2. Data Handling

Concentrations that are below the limit of quantitation (BLQ) prior to the first dose will be assigned a numerical value of zero. Post-treatment concentrations that are BLQ will be treated as missing.

Concentrations assigned a value of missing will be omitted from the descriptive statistics. A concentration value of zero will be excluded from the computation of the geometric mean (geometric CV%). If any subjects are found to be noncompliant with respect to dosing, have incomplete data, or encounter other circumstances that would affect the evaluation of pharmacokinetics, a decision will be made on a case-by-case basis as to their inclusion in the pharmacokinetic analysis. Data excluded from pharmacokinetic analysis will be included in the data listings, but not in the summaries.

In tables and listings for the derived pharmacokinetic data, there should be four decimal places for numerical values below 1, three decimal places for numeric values below 10 but above 1, and two decimal places for numeric values above 10. However, the listings of raw data should not have more decimal places than the actual data.

5.9.3. Noncompartmental Pharmacokinetic Analysis

Pharmacokinetic parameters of ACE-536 will be derived using noncompartmental analysis method with the software program Phoenix WinNonlin (version 6.2 or higher). The ACE-536 serum concentrations after the first dose (Cycle 1 Day 1 to Cycle 2 Day 1) will be used to estimate the drug serum exposure parameters within the first treatment cycle, and the ACE-536 serum concentrations after the final dose (Cycle 5 Day 1 to end of study), if sufficient, will be used to estimate the terminal elimination half-life in serum. Actual sampling and dosing times will be used in this analysis. The following noncompartmental pharmacokinetic parameters will be estimated:

T_{max}	Time to maximum observed serum concentration, obtained directly from the observed concentration-time data (for the first dose only)
C_{max}	Maximum observed serum concentration, obtained directly from the observed concentration-time data (for the first dose only)
AUC_{21d}	Area under the serum concentration-time curve from Day 1 to Day 21, calculated by the linear trapezoidal method (for the first dose only)
λ_z	Apparent terminal rate constant, calculated by linear regression of the terminal portion of the log-concentration-time curve in serum. Visual assessment may be used to identify the terminal linear phase of the log concentration-time profile. A minimum of 3 data points will be used for the calculation. The λ_z will not be estimated if the terminal phase of the log-concentration-time profile does not exhibit a linear decline phase, or if the regression coefficient (Rsq) is less than 0.8 (after the final dose)
$t_{1/2}$	Terminal elimination half-life in serum, calculated as $[(\ln 2)/\lambda_z]$. The terminal elimination half-life will only be calculated when a reliable estimate for λ_z can be obtained (after the final dose)

The following pharmacokinetic parameters will be calculated for diagnostic purposes and listed, but they will not be summarized:

λ_z lower: lower limit of time (days) included in the calculation of λ_z

λ_z upper: upper limit of time (days) included in the calculation of λ_z

λ_z N: number of data points used in the calculation of λ_z

Rsq: regression coefficient for calculation of λ_z

Additional noncompartmental pharmacokinetic parameters may be determined when appropriate.

